### 7.4. WINDOWING CONVENTIONS

No visit windowing will be performed for this study.

### 7.5. STATISTICAL TESTS

The default significance level will be 5%; confidence intervals (CIs) will be 95%. All p-values and CIs will be twosided, unless otherwise specified in the description of the analyses.

Document:	\\quintiles.net\enterprise\Apps\sasdata\SASa\sas\Sunovion\S 363856\BZA44200\Biostatistics\Documentation\SAP\V1\SEF	SEP- 2 361-301 SAP Final \	/1.0_26JUL2023
Author:		Version Number:	Final 1.0
		Version Date:	26JUL2023
Template No.:	CS_TP_BS016 Revision 5	Reference: C	CS_WI_BS005

Effective Date: 01Apr2018

PROTOCOL SEP361-118

Statistical Analysis Plan

Page 18 of 58

### 7.6. COMMON CALCULATIONS

For quantitative measurements, change from baseline will be calculated as:

Test Value at Visit X – Baseline Value

For PK computations, the Percentage Coefficient of Variation (CV%), Geometric Mean (GM), and Percentage Geometric Coefficient of Variation (GCV% or 'Geometric CV%') will be computed as below:

$$CV\% = 100 \frac{SD}{Mean}$$
$$GM = e^{Mean_{Log}}$$
$$GCV\% = (100)\sqrt{(e^{SD_{LOG}^2}) - 1}$$

Where SD is the sample standard deviation, Mean is the sample mean,  $Mean_{Log}$  is the sample mean of the log transformed data, and  $SD_{Log}$  is the sample standard deviation of the log transformed data. Note that when the data are lognormally distributed, CV% and GCV% are equal.

### 7.7. SOFTWARE VERSION

All analyses will be conducted using SAS version 9.4 or higher

### 7.8. MISSING DATA

No imputation will be performed for missing data.

### 7.9. EXAMINATION OF SUBGROUPS

No subgroup analyses will be performed for the analysis defined in this SAP.

### **8. OUTPUT PRESENTATIONS**

APPENDIX 1 shows conventions for presentation of data in outputs.

The templates provided with this SAP describe the presentations for this study and therefore the format and content of the summary tables, figures, and listings to be provided by IQVIA Biostatistics.

Document:	\\quintiles.net\enterprise\Apps\sasdata\SASa\sas\Sunovion\S 363856\BZA44200\Biostatistics\Documentation\SAP\V1\SEF	SEP- 2 361-301 SAP Final \	/1.0_26JUL2023
Author:		Version Number:	Final 1.0
		Version Date:	26JUL2023
Template No.:	CS_TP_BS016 Revision 5	Reference: C	CS_WI_BS005

Effective Date: 01Apr2018

### 9. DISPOSITION AND WITHDRAWALS

All subjects screened will be accounted for in this study.

The number and percentage of subjects screened, screen failed, and enrolled will be summarized for SEP-363856 (Overall) based on the number of all subjects screened. The number and percentage of subjects under each reason for screen failure will be presented based on the number of subjects screened. Number and percentage of subjects completing the study or terminating early will also be summarized (with reasons for early termination), based on the number of subjects included in the safety and efficacy populations will be presented, based on the number of enrolled subjects.

The number of subjects who failed screening due to COVID-19 related reasons and who discontinued early due to COVID-19 related reasons will be summarized in the disposition table. Subjects who failed screening or discontinued due to COVID-19 related AEs are identified by the following AEs with preferred terms (PTs) and codes:

- Coronavirus test positive (PT code = 10070255), or
- Corona virus infection (PT code = 10053983).

Disposition data will be provided in a listing for screen failures and all subjects enrolled.

### 9.1. IMPORTANT PROTOCOL DEVIATIONS

Important Protocol Deviations (IPDs) will be identified and documented based on a review of data listings and the protocol deviations log.

The IPD categories may include, but may not be limited to:

- Did not meet inclusion/exclusion criteria.
- Received any disallowed concomitant medication.

IPDs will be identified for all enrolled subjects and presented in a data listing. The number and percentage of subjects with IPDs will be summarized by category of deviation for SEP-363856 (Overall) for the safety population.

In addition, a listing of all protocol deviations reported by the clinical team during the study, including impact by COVID-19, will be provided for all subjects enrolled.

### **10.** DEMOGRAPHIC AND OTHER BASELINE CHARACTERISTICS

Demographic data and other baseline characteristics will be presented for the safety population and efficacy population. No statistical testing will be carried out for demographic or other baseline characteristics.

The number and percentage of subjects by gender, racial group and ethnicity will be summarized. Age, baseline height, baseline weight, baseline BMI, baseline efficacy parameters (PANSS total score, PANSS subscale scores (positive, negative, and general psychopathology), CGI-S score, BNSS total score, and MADRS total score) and baseline movement disorder measures (AIMS total score, BARS total score, and SAS mean score) will be summarized using descriptive statistics (number of subjects, mean and standard deviation, median, Q1, Q3,

Document:	\\quintiles.net\enterprise\Apps\sasdata\SASa\sas\Sunovion\SEP-				
	3030301DZA442001DI0Statistics1D0cumentation13AF1713EF	-301-301 SAF Fillal V	1.0_20J0L2023		
Author:		Version Number:	Final 1.0		
		Version Date:	26JUL2023		
Template No.:	CS_TP_BS016 Revision 5	Reference: C	S_WI_BS005		

Effective Date: 01Apr2018

Sumitomo Pharma PROTOCOL SEP361-118

#### Statistical Analysis Plan

minimum, and maximum).

Individual subject demographics and baseline characteristics will be presented in listings for all subjects enrolled.

### **10.1. DERIVATIONS**

• BMI  $(kg/m^2) = weight (kg)/height (m)^2$ 

### **11. MEDICAL AND PSYCHIATRIC HISTORY**

The medical history as well as psychiatric history of subjects will be coded by System Organ Class (SOC) and Preferred Term (PT) using the Medical Dictionary for Regulatory Activities (MedDRA), version 22.0. The number and percentage of subjects in each SOC and each PT will be summarized for the safety population for SEP-363856 (Overall).

Each subject's medical and psychiatric history will be listed by SOC and PT for all subjects enrolled.

### **12.** PRIOR AND CONCOMITENT MEDICATIONS

Subjects may not take any disallowed prescription or disallowed non-prescription medications, or dietary or herbal supplements, for at least 5 half-lives or 14 days prior to dosing, whichever is longer or anticipate the need for any disallowed medication during their participation in this trial. Concomitant use of CYP2D6 inhibitors is prohibited. Subjects may not use Clozapine for at least 120 days prior to PET scan at screening. Antidepressants, mood stabilizers, or anxiolytics [lorazepam or equivalent at doses above protocol-specified limits] are prohibited concomitant medications. Electroconvulsive therapy is prohibited within 3 months prior to screening and during the study.

Other than the study drug, any medication taken during the course of the study, with a start date/time on or after the first dose of study drug and on or before the last dose of study drug; or with a start date/time prior to, and an end date/time on or after, the first dose of study drug, or marked as ongoing, will be considered concomitant. Medications that stopped prior to the first dose of study drug will not be considered concomitant but prior medications. Post treatment medications are medications which started after the last dose of study drug.

Antipsychotic agents including depot neuroleptics taken within at least 6 months prior to screening, and any other medications taken within at least 3 months prior to screening, through the End of Study visit will be recorded and reported. All medications will be provided in a listing for all subjects enrolled.

All medications will be coded using the World Health Organization Drug Dictionary (WHODRUG version 01MAR2019). The number and percentage of subjects using each prior/concomitant medication will be summarized for safety population for SEP-363856 (Overall) according to the WHODRUG Anatomic Therapeutic Class (ATC) Level III and preferred name. Subjects with multiple uses of a prior/concomitant medication will be counted once for a given ATC class and preferred name.

Similarly, the number and percentage of subjects using background antipsychotics, including typical, atypical, oral and depot antipsychotics, will be summarized for safety population for SEP-363756 (Overall) according to the

Document:	\\quintiles.net\enterprise\Apps\sasdata\SASa\sas\Sunovion\S 363856\BZA44200\Biostatistics\Documentation\SAP\V1\SEF	SEP- 2 361-301 SAP Final V	/1.0_26JUL2023
Author:		Version Number:	Final 1.0
		Version Date:	26JUL2023
Template No.:	CS_TP_BS016 Revision 5	Reference: C	S_WI_BS005

Effective Date: 01Apr2018

WHODRUG Anatomic Therapeutic Class (ATC) Level III and preferred name. Background antipsychotics, including typical, atypical, oral and depot antipsychotics, are identified based on all prior/concomitant medications with "Started prior to study?" = "Yes" and "Ongoing"="Yes". The definitions of those medications are as below:

Category	Definition
Antipsychotics	ATC3 Code = N05A
Typical Antipsychotics	ATC4 Code = N05AA, N05AB, N05AC, N05AD, N05AF or N05AG
Atypical Antipsychotics	ATC4 Code = N05AE, N05AH, N05AL or N05AX
Oral Antipsychotics	ATC3 Code = N05A and "Route" = "oral"
Depot Antipsychotics	ATC3 Code = N05A and ("Route" = "intramuscular", "subcutaneous" or "other") and ("Frequency" = "As needed" or "other")

### **13.** STUDY MEDICATION EXPOSURE

The total number of days of exposure to study drug by dose level and for SEP-363856 (Overall) will be summarized categorically (N [%]) for the safety population. The total number of doses of exposure to radiotracer will be summarized categorically (N [%]) for the safety population as well.

A data listing, by subject, containing the study medication dosing data will be provided for all subjects enrolled.

### **14. STUDY MEDICATION COMPLIANCE**

Treatment compliance will not be summarized as all dosing will occur in-clinic.

### **15. EFFICACY OUTCOMES**

The analyses of the efficacy variables will be performed on the efficacy population, unless otherwise specified.

Document:	\\quintiles.net\enterprise\Apps\sasdata\SASa\sas\Sunovion\S 363856\BZA44200\Biostatistics\Documentation\SAP\V1\SEF	SEP- 2 361-301 SAP Final \	/1.0_26JUL2023
Author:		Version Number:	Final 1.0
		Version Date:	26JUL2023
Template No.:	CS_TP_BS016 Revision 5	Reference: 0	CS_WI_BS005

Effective Date: 01Apr2018

PROTOCOL SEP361-118

Statistical Analysis Plan

Page 22 of 58

### **15.1. EFFICACY VARIABLES**

Efficacy parameters include PANSS total score, PANSS subscale scores (positive, negative, and general psychopathology), PANSS factor scores (Marder factor scores and UPSM factor scores), CGI-S score, BNSS total score, BNSS subscale scores and MADRS total score. Tabular summaries will be based on the Efficacy Population.

The actual values and changes from baseline at each post-dose time point will be summarized, with 95% confidence intervals.

Efficacy parameters for each individual subject will be listed for all enrolled subjects.

#### PANSS

PANSS is used to measure the psychopathology in adults with psychotic disorders, comprising 30 items and 3 subscales. The positive subscale assesses hallucinations, delusions and related symptoms (7 items), the negative subscale assesses emotional withdrawal, lack of motivation and related symptoms (7 items), and the general psychopathology subscale assesses other symptoms such as anxiety, somatic concern and disorientation (16 items). An anchored Likert scale from 1 to 7 (1 = absent, 7 = extreme, with values of 2 and above indicating the presence of progressively more severe symptoms) is used to score each item. Individual items are summed to derive the following scores:

- Total score = sum of all 30 items. Total score ranges from 30 to 210.
- Subscale scores = sum of items within each of the following subscales:
  - Positive subscale: delusions, conceptual disorganization, hallucinatory behavior, excitement, grandiosity, suspiciousness/persecution, hostility. This subscale score ranges from 7 to 49.
  - Negative subscale: blunted affect, emotional withdrawal, poor rapport, passive/apathetic social withdrawal, difficulty in abstract thinking, lack of spontaneity and flow of conversation, stereotyped thinking. This subscale score ranges from 7 to 49.
  - General psychopathology subscale: somatic concern, anxiety, guilt feelings, tension, mannerisms and posturing, depression, motor retardation, uncooperativeness, unusual thought content, disorientation, poor attention, lack of judgment and insight, disturbance of volition, poor impulse control, preoccupation, active social avoidance. This subscale score ranges from 16 to 112.
- Marder factor scores sum of items within each of the following factors (Marder, Davis, Chouinard. 1997):
  - Negative symptoms: blunted affect, emotional withdrawal, poor rapport, passive/apathetic social withdrawal, lack of spontaneity and flow of conversation, motor retardation, active social avoidance
  - Positive symptoms: delusions, hallucinatory behavior, grandiosity, suspiciousness/persecution, stereotyped thinking, somatic concern, unusual thought content, lack of judgment and insight

Document:	\\quintiles.net\enterprise\Apps\sasdata\SASa\sas\Sunovion\	SEP-	
	363856\BZA44200\Biostatistics\Documentation\SAP\V1\SEF	2361-301 SAP Final	V1.0_26JUL2023
Author:		Version Number:	Final 1.0
		Version Date:	26JUL2023
Template No.:	CS_TP_BS016 Revision 5	Reference: (	CS_WI_BS005

Effective Date: 01Apr2018

- Disorganized thought: conceptual disorganization, difficulty in abstract thinking, mannerisms and posturing, disorientation, poor attention, disturbance of volition, preoccupation
- Uncontrolled hostility/excitement: excitement, hostility, uncooperativeness, poor impulse control
- o Anxiety/depression: anxiety, guilt feelings, tension, depression
- UPSM factor scores

The PANSS item scores of each subject at each visit will be transformed using the uncorrelated PANSS score matrix (UPSM), to obtain the scores of 7 transformed PANSS factors (Hopkins et al. 2018):

- POS: Positive
- DIS: Disorganized
- NAA: Negative apathy/avolition
- NDE: Negative deficit of expression
- HOS: Hostility
- ANX: Anxiety
- DEP: Depression

The transformation will be done as follows:

 $[PANSS Data]_{(N \times 30)} * [UPSM]_{(30 \times 7)} = [Transformed PANSS Factor Data]_{(N \times 7)}$ 

where

 $[PANSS Data]_{(N \times 30)}$  is matrix with N PANSS assessments and 30 columns containing the scores of 30 PANSS items ordered in the same way as shown in UPSM.

 $[UPSM]_{(30\times7)}$  is a matrix with 30 rows (one for each PANSS item) and 7 columns (one for each of the 7 transformed PANSS factors). This matrix is presented in Table 1.

[Transformed PANSS Factor Data] $_{(N\times7)}$  is the transformed matrix with N sets of scores for the 7 transformed PANSS factors

Document:	\\quintiles.net\enterprise\Apps\sasdata\SASa\sas\Sunovion\S 363856\BZA44200\Biostatistics\Documentation\SAP\V1\SEF	SEP- 2 361-301 SAP Final V	'1.0_26JUL2023
Author:		Version Number:	Final 1.0
		Version Date:	26JUL2023
Template No.:	CS_TP_BS016 Revision 5	Reference: C	S_WI_BS005

Effective Date: 01Apr2018

PROTOCOL SEP361-118

#### Statistical Analysis Plan

Page 24 of 58

Table 1 - Uncorrelated PANSS Score Matrix (UPSM) for Generating Transformed PANSS Factor Scores

PANSS	UPSM-POS	UPSM-DIS	UPSM-NAA	UPSM-NDE	UPSM-HOS	UPSM-ANX	UPSM-DEP
PANSS01	0.5792730597	-0.1547126840	-0.0828932650	0.0071927220	-0.0593031510	-0.0735449620	0.0020484408
PANSS02	0.0292444390	0.1975824582	-0.0260173260	-0.0234753800	-0.0368756010	-0.0012396240	-0.0361645050
PANSS03	0.2065788330	-0.0179419820	-0.0250663450	-0.0133031880	-0.0300507070	0.0001506005	0.0293001724
PANSS04	-0.0336790630	0.0115284348	0.0011652392	-0.0723891460	0.1379358628	0.1108194656	-0.1045224460
PANSS05	-0.0341508580	-0.0301875430	-0.0041019560	-0.0233459100	-0.0069204000	-0.0313277060	0.0308288417
PANSS06	0.3537254634	-0.0626270750	0.0477329954	0.0012126712	0.0192067437	-0.0161398140	0.0063264235
PANSS07	-0.0383468990	-0.1767919370	-0.0299340700	0.0314652864	0.5025411101	-0.0997121200	0.0573604084
PANSS08	-0.0054230270	-0.0291400280	0.0568702938	0.2474176209	-0.0388464000	0.0188235393	-0.0091524870
PANSS09	-0.0315765690	-0.0243925850	0.3317907576	-0.0228204580	-0.0507096280	-0.0145653830	0.0112689069
PANSS10	-0.0742072890	-0.0401313020	-0.0097485120	0.0161513666	0.0245536353	-0.0176161520	-0.0172218040
PANSS11	-0.0943532590	-0.0856364190	0.4611503804	-0.0286825100	-0.0189062390	-0.0185825180	-0.0130433890
PANSS12	0.0043338689	0.1062496353	0.0255910591	-0.0301470410	-0.0133497570	0.0096065791	-0.0686802390
PANSS13	0.0041274699	0.0051521898	0.0009558861	0.2576813501	-0.0085004640	0.0194235006	-0.1037459520
PANSS14	-0.0111267300	0.1462268689	-0.0276416260	0.0023017188	-0.0055291270	-0.0118427800	0.0040128786
PANSS15	-0.0356272010	0.0552508287	-0.0382627720	0.0110152489	-0.0309176290	0.0444944076	0.1059845189
PANSS16	-0.0331052830	-0.0821894470	-0.0327376640	-0.0533178140	-0.0386473380	0.4576579818	0.1197800301
PANSS17	-0.0368854600	-0.0004363100	-0.0020681500	-0.0407976460	-0.0272172130	-0.0253163640	0.2459654614
PANSS18	-0.0931367690	-0.0332617600	-0.0132943930	0.0231904701	-0.0287529750	0.5123850161	-0.0312522560
PANSS19	-0.0455199430	0.0494113554	-0.0324174560	0.1026255664	-0.0136676190	0.0293507269	-0.0441735260
PANSS20	-0.0344751890	-0.0688197670	-0.0412738350	0.0381793764	0.0042219619	-0.0635101090	0.4514426846
PANSS21	-0.0348890020	-0.0366137810	-0.0779782830	0.4409895205	-0.0073240410	-0.0192655290	0.0464131877

Document:	\\quintiles.net\enterprise\Apps\sasdata\SASa\sas\Sunovion\SEP- 363856\BZA44200\Biostatistics\Documentation\SAP\V1\SEP361-301 SAP Final V1.0_26.IUI 2023				
Author:		Version Number:	Final 1.0		
		Version Date:	26JUL2023		
Template No.:	CS_TP_BS016 Revision 5	Reference: C	S_WI_BS005		

Effective Date: 01Apr2018

PROTOCOL SEP361-118

Statistical Analysis Plan

Page 25 of 58

PANSS22	-0.0803690920	0.0334025939	-0.0088488890	-0.0200483170	0.2858700784	-0.0567167860	-0.0531076130
PANSS23	0.1428966744	0.0939213700	-0.0326143600	-0.0367524640	-0.0675856980	-0.0209072840	-0.0177890070
PANSS24	-0.0383047770	-0.0324584080	-0.0255393890	-0.0180115340	-0.0266180700	-0.0210068530	-0.0176029110
PANSS25	-0.1036311520	0.2814367260	-0.0478918640	0.0029986238	0.0037656449	-0.0226520240	0.0401351054
PANSS26	0.0142987589	0.1548635741	-0.0306089330	-0.0331581690	0.0262295986	-0.0576293550	-0.0626180490
PANSS27	-0.0573513270	0.1867914227	-0.0143489160	0.0581534153	-0.0145494330	-0.0371788310	0.0455412078
PANSS28	-0.0748387810	0.0166272025	-0.0267498020	-0.0031632780	0.2546669938	-0.0201249190	-0.0076420280
PANSS29	-0.0520812460	0.2912295497	0.0029775475	-0.0324350460	-0.0442337350	-0.0047991290	0.0567191230
PANSS30	-0.0112030990	-0.0007246980	0.2860136812	-0.0606201430	0.0183598393	-0.0302347770	0.0370748725

 

 Document:
 \\quintiles.net\enterprise\Apps\sasdata\SASa\sas\Sunovion\SEP-363856\BZA44200\Biostatistics\Documentation\SAP\V1\SEP361-301
 SAP Final V1.0\_26JUL2023

 Author:
 Version Number:
 Final 1.0

 Version Date:
 26JUL2023

 Template No.:
 CS\_TP\_BS016 Revision 5
 Reference:
 CS\_WI\_BS005

Effective Date: 01Apr2018

Sumitomo Pharma PROTOCOL SEP361-118

Page 26 of 58

#### CGI-S

The CGI-S is a clinician-rated assessment of the subject's current illness state on a 7-point scale, where a higher score is associated with greater illness severity. The CGI-S score takes one of the following values: 1 (normal, not at all ill), 2 (borderline mentally ill), 3 (mildly ill), 4 (moderately ill), 5 (markedly ill), 6 (severely ill), 7 (among the most extremely ill patients).

#### BNSS

The BNSS is a rating scale to measure the current level of severity of negative symptoms in schizophrenia and schizoaffective disorder. The measure is comprised of 13 individual items organized in 6 subscales (blunted affect (items 9, 10, 11), alogia (items 12, 13), avolition (items 7, 8), anhedonia (items 1, 2, 3), asociality (items 5, 6), and distress (item 4)). The 13 individual items provide a composite total score (ranging from 0 to 78). Each of the items is scored on a Likert-type 7-point scale from 0 - 6, where a value of 0 indicates symptom is absent and a value of 6 means the symptom is a severe form. In addition, BNSS subscale scores will be calculated by summing the item scores under each subscale.

#### MADRS

The MADRS is a clinician-rated assessment of the subject's level of depression. The measure contains 10 items that measure apparent and reported sadness, inner tension, reduced sleep and appetite, difficulty concentrating, lassitude, inability to feel, and pessimistic and suicidal thoughts. Each item is scored in a range of 0 to 6 points, with higher scores indicating increased depressive symptoms. MADRS total score will be calculated by the sum of all 10 item scores.

### **15.2. MISSING DATA METHOD FOR EFFICACY VARIABLES**

The PANSS total score, PANSS subscale scores (positive, negative, and general psychopathology), PANSS factor scores (Marder factor scores and UPSM factor scores), BNSS total score, BNSS subscale scores and MADRS total score will be set to missing if any one item contributing to the total/subscale/factor score is missing. The change from baseline in PANSS total score, PANSS subscale scores (positive, negative, and general psychopathology), PANSS factor scores (Marder factor scores and UPSM factor scores), CGI-S score, BNSS total score, BNSS subscale scores and MADRS total score, BNSS subscale scores and MADRS total score at Week 2 (Day 14 or ET), will be set to missing if such scores at baseline or at Week 2 (Day 14 or ET) is missing. Missing data will not be imputed.

### **16.** SAFETY OUTCOMES

All tabular summaries for safety outcomes will be based on the safety population.

### **16.1. ADVERSE EVENTS**

AEs will be coded using Medical Dictionary for Regulatory Activities (MedDRA) central coding dictionary, Version 22.0.

An AE can be any unfavorable and unintended sign (including an abnormal laboratory finding), symptom, or disease

Document:	ment: \\quintiles.net\enterprise\Apps\sasdata\SASa\sas\Sunovion\SEP- 363856\BZA44200\Biostatistics\Documentation\SAP\V1\SEP361-301 SAP Final V1.0_26JUL20:					
Author:		Version Number:	Final 1.0			
		Version Date:	26JUL2023			
Template No.:	CS_TP_BS016 Revision 5	Reference: C	S_WI_BS005			

Effective Date: 01Apr2018

occurring after signing the informed consent form (ICF), whether or not considered related to the medicinal (investigational) product. AEs may include the onset of new illness and the exacerbation of pre-existing conditions. AEs will be collected from the time of signing the ICF to the last study visit/EOS visit.

TEAEs are untoward medical occurrences:

- that occurred on or after the first dose of study medication,
- with a missing start date and a stop date on or after the first dose of study medication, or
- with both a missing start date and a missing stop date.

The following TEAEs will be summarized and presented by MedDRA SOC and PT for the Safety population:

- All TEAEs (including number of events and subject incidence).
- TEAEs by severity (mild, moderate, severe).
- TEAEs by relationship to the study treatment (related, or not related).
- TEAEs by dose at onset (including number of events and subject incidence)
- TEAEs leading to study medication discontinuation (including number of events and subject incidence)
- Serious TEAEs (including number of events and subject incidence)
- TEAEs leading to study discontinuation (including number of events and subject incidence)

The following conventions will be followed in summarizing TEAEs:

- For subject incidence summaries, each subject will be counted only once within each SOC and within each preferred term.
- If a subject reports more than one TEAE within a preferred term and/or a body system, the adverse event with the highest known severity within each body system and within each preferred term will be included in the summaries by severity. Any TEAE with a missing severity will be treated as "severe" and counted in the severe category.
- For summaries by relationship to study drug, TEAEs assessed as "possible," "probable," or "definite" will be grouped as "related." If a subject reports more than one TEAE within the same treatment regimen, SOC and PT, and any are related, it will be summarized as related. Any TEAE with a missing relationship to study medication will be regarded as "related" to study medication.
- For summaries by dose at AE onset, TEAEs will be summarized by the last actual dose level the subject was on before the onset of event. If a subject reports more than one TEAE within the same dose level, SOC and PT, it will be counted only once.

Untoward medical occurrences that occur between the time of signing the ICF and first drug administration are pre-treatment events.

A listing of AEs (TEAEs and pre-treatment events), as well as a listing of Serious TEAEs, TEAEs leading to discontinuation of study medication and discontinuation from study, TEAEs of potential drug abuse and dependence (see APPENDIX 6), and a listing of treatment emergent deaths will be presented.

See APPENDIX 2 for handling of partial dates for AEs. In the case where it is not possible to determine whether an AE began before or after dosing, the AE will be classified by the worst case; i.e. treatment emergent.

Document:	ocument:         \\quintiles.net\enterprise\Apps\sasdata\SASa\sas\Sunovion\SEP-           363856\BZA44200\Biostatistics\Documentation\SAP\V1\SEP361-301         SAP Final V1.0_26JUL:					
Author:		Version Number:	Final 1.0			
		Version Date:	26JUL2023			
Template No.:	CS_TP_BS016 Revision 5	Reference: C	S_WI_BS005			

Effective Date: 01Apr2018

Presentations regarding each of the categories described in the sub-sections below, will be provided as described and specified in the templates.

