#### **10.1.1. Dose Adjustment Criteria**

Subjects will receive SEP-363856 50 mg/day on Day 1 through Day 3. On Day 4, subjects will titrate up to a dose of 75 mg/day. Subjects may dose reduce one time to 50 mg/day for tolerability reasons at any time. Subjects who have a dose reduction for tolerability will continue to receive the reduced dose for the remainder of the study.

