#### **PRESENTATION OF TREATMENT GROUPS**

For outputs, treatment groups will be represented as follows and in that order unless shown otherwise in the output templates:

Treatment Group	For Tables and Graphs	For Listings
SEP-363856 (Overall)	SEP-363856 (Overall)	SEP-363856 (Overall)

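### The SAP 16.1 table of TEAEs by dose at onset is confounded by exposure time, time since first dose and dose reduction, and could mislead in either direction

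*SAP*

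**What the plan says.** SAP 16.1 lists a table of "TEAEs by dose at onset (including number of events and subject incidence"), by system organ class and preferred term in the safety population. Two rules govern it. Attribution: "TEAEs will be summarized by the last actual dose level the subject was on before the onset of event". Counting: "If a subject reports more than one TEAE within the same dose level, SOC and PT, it will be counted only once". SAP 16.1.1 repeats the table, presented for the overall treatment group. Protocol 15.3.8.1 does not list such a table, so it is an addition made in the SAP.

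Protocol 10.1.1 fixes the sequence: "Subjects will receive SEP-363856 50 mg/day on Day 1 through Day 3. On Day 4, subjects will titrate up to a dose of 75 mg/day". Dosing ends on Day 14 or, if the scan has to be repeated, by Day 19 (Protocol 7.1). One reduction to 50 mg for tolerability is allowed and is kept to the end of the study. Under SAP 16.1, adverse events are collected up to the last visit, and the treatment-emergent definition sets no end limit. The follow-up visit falls 7 ± 2 days after the last dose (Protocol 7.1 and 11.9.3).

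SAP 13 plans a separate exposure table: "The total number of days of exposure to study drug by dose level and for SEP-363856 (Overall) will be summarized categorically". No rate per unit of exposure is planned anywhere. SAP text does not state the denominator for the dose-at-onset percentages.

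**The concern.** Three features of the rule prevent a like-for-like reading of the two dose levels.

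- **Unequal time at risk.** Every subject has a short, fixed spell at starting 50 mg, and most will then have a much longer one at 75 mg. Counts and incidence grow with time at risk whatever the dose does.
- **Off-drug events.** With no cut-off after the last dose, an event starting during follow-up is credited to the dose last taken: 75 mg for subjects not reduced, 50 mg for those reduced.
- **Two different 50 mg states.** The level 50 mg combines all subjects at first exposure with the subset moved down because they tolerated 75 mg poorly. Dose is also tied to time since first dose, because 50 mg comes first for everyone.

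Apart from the exposure table, this is the only safety output the SAP splits by dose. SAP 4.2 replaces the protocol's dose-group and dose-cohort summaries of deviations, laboratory values and orthostatic hypotension with overall summaries. The safety objective names 50 or 75 mg/day, so readers interested in tolerability at either dose will go to this table.

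**Working it through.** The plan gives no adverse event rate, person-time or by-dose denominator, so there is no figure to reproduce. The check asks what the stated rule would produce if dose had no effect.

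**Inputs from the documents**
- Starting 50 mg: Days 1 to 3, so 3 days (Protocol 10.1.1).
- 75 mg without reduction: 14 − 3 = 11 days, or 19 − 3 = 16 days if dosing runs to Day 19 (Protocol 7.1).
- Off-drug follow-up: 7 days, window 5 to 9 (Protocol 7.1, 11.9.3).
- Planned subjects: 22 (Protocol 15.1).

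**Assumptions, not in the documents**
- Daily hazard h of a first event: 0.005 to 0.10 per subject-day, the same at both doses and continuing through follow-up.
- Share of subjects reduced and day of reduction: illustrative values only.

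**Step 1. Event counts, constant hazard, no reductions.** Expected events = h × days, so h cancels and the 75:50 ratio is the ratio of days.
- On drug to Day 14: 11/3 = 3.67.
- On drug to Day 19: 16/3 = 5.33.
- To Day 14 plus 7 follow-up days: 18/3 = 6.0.
- Longest case, Day 19 plus 9 follow-up days: 25/3 = 8.33.

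**Step 2. Subject incidence.** Incidence = 1 − exp(−h × days). At h = 0.02:
- 50 mg: 1 − exp(−0.06) = 5.8%, about 1.3 of 22 subjects.
- 75 mg on drug: 1 − exp(−0.22) = 19.7%, about 4.3 of 22; ratio 3.39.
- 75 mg with 7 follow-up days: 1 − exp(−0.36) = 30.2%, about 6.7 of 22; ratio 5.19.

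From h = 0.005 to h = 0.10 the incidence ratio runs from 3.59 down to 2.57 on drug, and from 5.78 down to 3.22 with follow-up.

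**Step 3. Higher hazard at first exposure.** Let the hazard on Days 1 to 3 be k times the later one. The event ratio becomes 11/(3k) on drug, or 18/(3k) with follow-up. Counts are equal at k = 3.67 and k = 6.0 respectively. At k = 5 the ratios are 11/15 = 0.73 and 18/15 = 1.20, so on drug 50 mg would look worse.

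**Step 4. Reductions.** If a share r is reduced from Day R and the follow-up counted is F days, average days per subject are
- 50 mg: 3 + r × [(15 − R) + F]
- 75 mg: (1 − r) × (11 + F) + r × (R − 4)

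| r, R | F | Days at 50 mg | Days at 75 mg | Ratio |
|---|---|---|---|---|
| 25%, Day 8 | 0 | 4.75 | 9.25 | 1.95 |
| 25%, Day 8 | 7 | 6.50 | 14.50 | 2.23 |
| 50%, Day 5 | 0 | 8.00 | 6.00 | 0.75 |
| 50%, Day 5 | 7 | 11.50 | 9.50 | 0.83 |

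Pooling reduced 50 mg therefore works against the Step 1 gradient and can reverse it.

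**Step 5. What a rate corrects.** With events divided by on-drug subject-days at each level, a constant hazard gives (11h/11)/(3h/3) = 1.0. The rate does not remove confounding with time since first dose: in the Step 3 case with k = 5, the rate ratio would be h/(5h) = 0.2 with no dose effect.

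**The case against.** The strongest defence is that nobody plans to compare doses. Safety is descriptive, no test of dose-response is specified, and the safety objective does not ask for a contrast between 50 and 75 mg. Exposure days by dose level are tabulated under SAP 13, and dosing and adverse events are listed by subject, so a careful reader could recover the context. In about 22 subjects, four onset rows by organ class and preferred term will leave many sparse cells. Rates cannot cure confounding by time since first dose or selection into reduction.

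Most of this stands, and it limits the severity. It does not make the by-dose incidences interpretable: the exposure table is separate and categorical, and puts no person-time beside the event counts.

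Two stronger readings are tempting and are not supported.

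- A reader might infer that the table will show a dose-response where none exists. The documents do not say whether a dose effect exists. They give neither the timing of events nor the share of subjects reduced, and Steps 3 and 4 show that the distortion can run either way.
- A reader might infer that both dose levels must share one denominator, because SAP Appendix 1 defines only the overall group. That appendix yields to output templates, which are not part of the text. Appendix 5 also requires either a row giving the count used or a footnote naming the denominator. The SAP text leaves the denominator unstated; it does not state a wrong one.

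**Conclusion.** The point holds as a minor one. Under the attribution rule as written, the two dose levels differ in time at risk, in time since first dose and, for 50 mg, in how subjects came to be there. The figures are not comparable between doses.

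The day counts, 3 against 11 to 16 plus 5 to 9 follow-up days, come from the documents. The ratios of 3.67 on drug and 6.0 with 7 follow-up days rest on a constant hazard, no dose effect and no reductions; the second also assumes that the hazard continues off drug. The incidence percentages rest in addition on assumed hazards and are illustrations only. With more events on Days 1 to 3, or many early reductions, the apparent difference shrinks or reverses, so no direction of bias can be asserted in advance.

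The table can still describe which events began after which dose. It cannot support a statement that one dose is better tolerated than the other. The primary endpoint is unaffected.

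**What to change.** In SAP 16.1 and 16.1.1:

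1. Present onset in four separate categories: on starting 50 mg, on 75 mg, on 50 mg after reduction, and after the last dose. State the rule that separates the last category from on-drug onset.
2. Use subjects exposed at each level as the percentage denominator, and say so in the SAP text. For the last category, use subjects followed after their last dose.
3. Show subject-days and events per 100 subject-days for each category, at least for any TEAE. The by-dose exposure days needed for SAP 13 supply the base, with days at 50 mg split into before and after reduction and follow-up days counted separately.
4. Add a footnote that dose is confounded with time since first dose and with selection into reduction, and that no dose comparison is intended.

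The cost is SAP wording and a little more programming on data already collected. The downside is sparse cells, mainly in the reduced-dose category; limiting the rates to any TEAE keeps that manageable.
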